5.4.4 Accrual

We anticipate accruing 120 patients within 3 years.

5.5 Data Safety and Monitoring Plan

5.5.1 Plan for monitoring the progress of the trial and the safety of participants

- As this is not an experimental therapeutic trial, and the risks and discomforts are expected to be small (see section 6.2), the PI will assume primary responsibility for monitoring the progress of the trial and the safety of participants.
- As part of the NCI CCR, this trial may be selected at random to be monitored by the staff of Harris Technical Services Corporation
- Data will also be submitted to the NCI IRB annually for continuing review and at the completion of the study.
- In addition, at monthly research/ protocol meetings, senior staff of the NCI ROB will review protocol progress and provide feedback to the PI.

5.5.2 Plan for assuring the compliance with the requirements for reporting adverse events

- Adverse events will be reported as in section 5.3 and 7.3

5.5.3 Plan for assuring that any action resulting in suspension of the trial is reported to the IRB

- As this is an intramural NCI CCR protocol without external sponsors, the NCI IRB would be responsible for issuing the suspension and would therefore necessarily be aware.

5.5.4 Plan for assuring data accuracy and protocol compliance

- Data will be collected as in section 5.1
- Research data and acquired samples will be recorded in the NCI CCR C3D database.
- Data integrity and protocol adherence are assured by regular data verification and protocol compliance checks performed by the research team (PI, research nurse, data manager and clinic nurse).

6.0 HUMAN SUBJECTS PROTECTION

6.1 RATIONALE FOR SUBJECT SELECTION:

6.1.1 The racial ethnic and gender makeup of the study population is that of the population of the patients seen in the Radiation Oncology Branch, NCI. No racial or ethnic group is excluded. Adults who are cognitively impaired prior to study entry must have already assigned a DPA or will not be eligible for study entry because they cannot give informed consent.

6.2 Participation of children: Children younger than 18 will not be included.

6.3 EVALUATION OF RISKS/DISCOMFORTS:

6.3.1 This is not an experimental therapeutic trial, and so risks and discomforts are expected to be small and related only to the risks of obtaining the blood samples, biopsies, and the intestinal permeability assessment. Venipuncture is a minimal risk procedure, which may include pain or bruising around the site of the needle puncture, and a small risk of fainting or of infection of the site.

6.3.2 Any side effects from the radiotherapy will be outlined in separate radiation oncology branch consent for radiation form.

6.3.3 Biopsy

The risks of endoscopic biopsies and percutaneous biopsies are low, and are procedures that are performed routinely by many of the associate investigators for staging or diagnostic purposes for this patient population. These potential risks and benefits will be carefully discussed with the patient at the time consent is obtained. Consent will be obtained separately for the biopsy procedure if one is required.

6.3.4 Intestinal Permeability Assessment

The intestinal permeability assessment may cause in some individuals intestinal cramping or diarrhea. These symptoms are uncommon and typically resolve within 24 hours of the test.

6.4 Risk/Benefit Analysis

The patients will derive no direct benefit from the procurement of biopsy tissue, blood, urine, and/or stool, and that will be clearly stated in the protocol consent document. In the course of the investigation, should any information from the blood, urine, or stool testing emerge that might benefit patient treatment for the primary disease process or any toxicity of treatment; we would attempt to inform the patient, after discussion with Medical Ethics consultation and the IRB. The risks to the patients participating in this trial are anticipated to be small, and are primarily the risks associated with appropriate staging procedures, biopsies (ie gi endoscopies), and subsequent multidisciplinary therapy for their malignancies. Specifically, the risks of endoscopic biopsies and percutaneous biopsies are exceedingly low, and are procedures that are performed routinely by many of the associate investigators for staging or diagnostic purposes for this patient population. These potential risks and benefits will be carefully discussed with the patient at the time consent is obtained. If a biopsy is considered to be more than minimal risk based on the location of the tumor (ie pancreatic tumors with no invasive procedures or surgical procedures planned) than biopsy may be omitted.

6.5 CONSENT AND ASSENT PROCESSES:

The investigational nature, the research objectives of this trial, and the blood and/or urine collection procedure will be carefully explained to the patients. Attendant risks and

discomforts will be described. The patients will be asked to read the consent and will be encouraged to ask questions. Patients will be enrolled after eligibility criteria have been reviewed, and after the consent document has been signed. Children will not be enrolled onto this study.

6.6 PATIENT ADVOCATE

The patient's rights representative is available to patients on this protocol at [contact] in [name], NIH. Patients may ask any questions about the study and may withdraw their consent at any time without compromising their medical care.

7.0 DATA REPORTING

7.1 PATIENT REGISTRATION FORM

Demographic information and results of pretreatment studies should be entered and reported to Central Registration office at the time of patient entry onto the trial (see section 2.3).

7.2 DATA SUBMISSION

- Summary information will be submitted to the IRB annually for continuing review and at the completion of the study.
- Data may be reported in laboratory publications as derived from this study. Patients will not be indicated by name.

7.3 SAFETY REPORTING

7.3.1 As this is intended as a companion study to standard radiotherapy, adverse events occurring while on study should be reported in the patient's primary experimental protocol.

7.3.2 For toxicites related to the procedures associated with this protocol

- Toxicity will be graded as indicated in Section 5.3
- Expected acute side effects from radiotherapy treatment and/ or progression of disease will not be reported as adverse events, except grades 4 or 5.
- For all other adverse events, occurring during the active treatment phase and for 30 days thereafter, the NCI-IRB Adverse Event Reporting Requirements will apply. The PI will report:
 - All serious events as defined by the FDA that are unexpected and related to the research;
 - All deaths (Grade 5: CTCAE) expected and unexpected, related and unrelated to the research; and
 - All Grade 3 and 4 (CTCAE), unexpected, and related to the research with attributions of possibly, probably, or definitely,

within 7 calendar days.

- The NCI-IRB requires a summary report of adverse events that have occurred on the protocol since the previous continuing review. The method of presentation should provide the NCI-IRB with the information necessary to clearly identify risks to participants and to make a risk:benefit determination. The summary report is based on the following guidance:

Any unexpected severity and/or unexpected frequency of expected events needs to be reported and interpreted in relation to the risk:benefit of study participants in the narrative.

1. Grade 1 events are not required.
2. Grade 2 unexpected related to the research events is required.
3. Grade 3 and 4 expected and unexpected events related to the research are required.
4. All Serious Events regardless of attribution.
5. Grade 5 (all) events are included regardless of attribution.

- Based on protocol-associated risks to participants, the NCI-IRB retains the authority to establish more frequent Continuing Review periods more frequently than the customary annual review period.
- After 30 days, only unexpected, late- radiation toxicities will be reported, with the exception of deaths on study, which will continue to be reported, regardless of cause, in order to provide survival data.

7.3.3 *Serious Adverse Events*

- **Serious Adverse Event (SAE) or Serious Adverse Drug Reaction (Serious ADR)**
Any untoward medical occurrence that at any dose:
 - results in death,
 - is life-threatening,
 - requires inpatient hospitalization or prolongation of existing hospitalization,
 - results in persistent or significant disability/incapacity, or
 - is a congenital anomaly/birth defect
- All serious adverse events must be reported to [name], Principal Investigator of this study and to NCI IRB **within 7 calendar days in writing** using the NCI AE form.

[name], PI
NCI, ROB
[name]

NCI IRB
c/o [name]
[name]

[contact]
 [contact]

[name]
 [contact]
 [contact]

- In addition, the following reactions occurring during or within 30 days of active protocol treatment should be within 7 calendar days to [name], MD the Principal Investigator, and to the NCI IRB
 - All life-threatening events (grade 4, Common Toxicity Criteria, version 2.0) which may be due to protocol therapy administration
 - All fatal events (grade 5, CTC version 2.0) while on study (or within 30 days of active treatment)
 - First occurrence of any previously unknown clinical event (regardless of grade)

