3.3 ON STUDY EVALUATION

3.3.1 Pre-Treatment (baseline)

- Informed consent obtained
- Clinical evaluation

See 2.2.1

Baseline acute RTOG toxicity assessment (appendix IIIA)

- Laboratory Evaluation

See 2.2.2

Hepatitis B

Hepatitis C

CBC, ALT, AST, total bilirubin, serum BUN, serum creatinine

- Research Specimen Collection:

- Blood, urine, stool (see 3.2.1.2)
 - baseline intestinal permeability test, 6 hour urine (see 3.2.2)

- Pathologic confirmation and biopsy of tumor tissue (see 2.2.3)

3.3.2 *Radiation Treatment Phase*

- Patients will receive radiotherapy for carcinoma of the esophagus, stomach, pancreas, bile ducts, or rectum on an NCI protocol
- At completion of radiation (within the final five fractions)
 - Research Specimen Collection:
 - Blood, urine, stool (see 3.2.1.2)
 - Toxicity Evaluation: RTOG - Acute Radiation Morbidity Scoring Criteria (Appendix IIIA)

3.3.3 *Post Active Treatment Evaluation (follow- up)*

- 3.3.3.1 Patients will be seen for routine follow-up at 1, 3, 6 and 12, 24, and 36 months post-radiotherapy.

- 3.3.3.2 These follow- up visits will include:

- Clinical Evaluation
 - A complete history and physical exam detailing the patient's disease status, bowel function, and medication requirements related to gastrointestinal toxicity. All post-radiotherapy adjuvant therapy will be recorded.
 - Toxicity Evaluation: Complete RTOG - Radiation Morbidity Scoring Criteria (Appendix IIIA, acute at 1 month and IIIB, late at 3, 6, and 12, 24, and 36 months follow-up.
- Laboratory Evaluation
 - As clinically indicated. The presence of accepted serum tumor markers (ie CA 19-9) in excess of defined maximum ranges will be recorded as evidence of disease recurrence.
 - CBC, ALT, AST, total bilirubin, serum BUN, serum creatinine
- Research Specimen Collection:
 - Blood, urine, stool (see 3.2.1)
 - intestinal permeability test, 6 hour urine (see 3.2.2) AT ONE AND THREE MONTHS ONLY
- Radiologic Evaluation
 - As clinically indicated by primary site and primary protocol. For the purpose of radiographically evaluating disease status to correlate to laboratory findings the following radiographic evaluations may be included for determination of disease recurrence: CT, plain films, bone scans, MRI, US, and PET.
- Response Category Evaluation (as in 5.2)

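### The 7-day reporting window in Section 7.3.2 does not fit the schedule of the study's own procedures, and its post-30-day sentence contradicts two other reporting rules

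*Combined protocol and SAP*

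**What the plan says.** - Section 6.3.1 describes the study's risks as "related only to the risks of obtaining the blood samples, biopsies, and the intestinal permeability assessment".
- Section 7.3.2 is headed as dealing with toxicities "related to the procedures associated with this protocol". Its operative rule is: "For all other adverse events, occurring during the active treatment phase and for 30 days thereafter, the NCI-IRB Adverse Event Reporting Requirements will apply". The 7-day list that follows holds unexpected related serious events, all deaths, and unexpected related grade 3–4 events.
- The same section then sets out an annual IRB summary. It requires unexpected related grade 2 events, all related grade 3–4 events, serious events whatever their attribution, and all grade 5 events. It covers the time since the last review and has no treatment-phase window.
- Section 7.3.2 closes with: "After 30 days, only unexpected, late- radiation toxicities will be reported, with the exception of deaths on study".
- Section 7.3.3 opens its reporting rule with "All serious adverse events must be reported to" the principal investigator and the IRB within 7 calendar days, and gives no start or end. A further list there is limited to active protocol treatment and the 30 days after it.
- Section 7.3.1 sends on-study adverse events to the patient's primary treatment protocol.

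**The concern.** The section written for the research procedures takes its clock from a treatment phase, and most of the research procedures are not done in that phase. Tissue and the first samples are taken before any therapy, and follow-up samples run to month 36. A reporting window should follow the exposure it monitors.

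The principal investigator carries primary responsibility for safety monitoring (Section 5.5.1), and Section 6.4 rests on the study's risks being small. Prompt IRB reports are one of the checks on that premise. If staff follow the closing sentence of 7.3.2 literally, an unexpected reaction to the 3-month challenge is not reportable under that sentence, although two neighbouring rules may say that it is.

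**Working it through.** The plan gives no figure to reproduce. The check sets the schedule against the window.

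**1. What the phase means.** Section 7.3 does not define it. Section 3.3 runs from Pre-Treatment (3.3.1) to Radiation Treatment Phase (3.3.2) to "Post Active Treatment Evaluation (follow- up" (3.3.3). Section 3.3.3 contains the follow-up permeability tests, marked "AT ONE AND THREE MONTHS ONLY". The protocol therefore places those tests after active treatment. The most natural reading is that active treatment is radiotherapy and that the window closes 30 days after it ends.

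**2. Schedule against window.** The follow-up visits are timed from radiotherapy (3.3.3). I assume that 1 month is 28–31 days and 3 months is 89–92 days (28+31+30 to 31+31+30).

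| Procedure (Sections 3.1.1, 3.2, 3.3) | Timing | Against the window |
|---|---|---|
| Research biopsy, if done | before treatment | before it opens |
| Baseline challenge | before any therapy | before it opens |
| 1-month challenge | day 28–31 | on the day-30 edge |
| 3-month challenge | day 89–92 | 59–62 days after it closes |
| Draw at completion of radiotherapy | final five fractions | inside |
| 1-month draw | day 28–31 | on the edge |
| Draws at baseline, 3, 6, 12, 24 and 36 months | before or after | outside |

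**3. Counts per patient with full attendance.**
- Challenges: 2 of the 3 in Section 3.2.2.2 are outside, 1 is on the edge, and none is clearly inside. Section 3.1.1 adds a separate pre-radiotherapy test where that differs from baseline, which makes 3 of 4 outside.
- Draws: baseline, completion, 1, 3, 6, 12, 24 and 36 months make 8. Outside are baseline plus five late draws, 1 + 5 = 6 of 8. A separate pre-radiotherapy draw makes 7 of 9.
- A patient who never starts radiotherapy goes off study (3.6.3). For that patient the window never opens, although a biopsy and a challenge may have been done.

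**4. Sensitivity to the reading.** If the phase means any anti-cancer therapy, the biopsy, baseline challenge and baseline draw still come before it. A separate pre-radiotherapy draw could then be inside. The status of the 3-month challenge would depend on whether adjuvant treatment followed radiotherapy, which Section 3.4 allows. If the phase means all research procedures, nothing is outside.

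**5. What is lost for a procedure outside the window.**

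| Event | 7-day route | Annual summary |
|---|---|---|
| Death | kept | yes |
| Serious | kept by 7.3.3, denied by the closing sentence of 7.3.2 | yes |
| Non-serious, unexpected, related grade 3–4 | **lost** | yes |
| Non-serious, expected, related grade 3–4 | not on the 7.3.2 list even inside the window | yes |

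Section 7.3.3 itself describes grade 4 as life-threatening, which is one of its criteria for a serious event. The lost row is therefore mainly grade 3. The further list in 7.3.3 has the same 30-day limit and does not fill the gap.

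**The case against.** The strongest reply is that little is actually lost. Serious events go to the IRB within 7 days with no window. The annual summary takes related grade 3–4 and unexpected related grade 2 events whenever they occur. Section 7.3.1 also sends on-study events to the primary protocol, and every patient must be treated on an NCI protocol (2.1.1.3). Nothing says that the window limits what is recorded, and each follow-up visit includes a full history and examination. The known reactions to the challenge, cramping and diarrhea (6.3.4), would not be on the 7-day list in 7.3.2 even inside the window, because that list requires the event to be unexpected. All of this stands, and it sets the size of the point.

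The reply continues that the phase need not be radiotherapy. Section 3.2 is headed as protocol therapy administration and contains the tissue, blood and permeability procedures, and 7.3.3 uses similar words. The ambiguity is real. But a phase that ran through every research procedure would reach month 36, when patients leave the study (3.6.4), and the closing sentence would then have almost nothing to govern. It would also contradict the title of Section 3.3.3. The IRB's own requirements, which 7.3.2 invokes, are not in the documents and might be broader.

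The other routes do not remove the conflict. The closing sentence says that only two kinds of event are reported after 30 days. It comes after the summary list in the same section, and nothing states which rule governs. The primary protocol is not a substitute for the section this study wrote for its own procedures.

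**Conclusion.** The point holds as a mismatch and a contradiction in the safety-reporting rules. On the radiotherapy reading, the window leaves out any research biopsy, two of three challenges, and 6 of 8 draws (7 of 9 with a separate pre-radiotherapy draw). The firm consequence is that non-serious, unexpected, research-related grade 3–4 events from those procedures lose the 7-day clock. In addition, the closing sentence of 7.3.2, read literally, conflicts with the unlimited serious-event rule in 7.3.3 and with the annual summary. These passages must be reconciled. No endpoint or analysis is affected.

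This rests on an inference from headings about an undefined term, and on follow-up visits held close to schedule. The baseline part also holds if the phase means any anti-cancer therapy.

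A reader might infer that the study would miss most harms of its own procedures, or that they would go unreported. The documents do not support that. The serious-event rule, the annual summary and the primary protocol all remain. The counts above are shares of procedures, not of events, and no event rate is given. Nor does every patient have a research biopsy: adequate existing tissue suffices (2.1.1.4), and patients for whom a biopsy exceeds minimal risk are exempt (3.2.1.1.1).

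**What to change.** 1. Define *active treatment phase* in Section 7.3.
2. In 7.3.2, make reporting of research-related events run from consent through the last study procedure.
3. Limit the post-30-day sentence to radiotherapy- and disease-related events.
4. State that this sentence limits neither the annual summary nor the serious-event rule in 7.3.3. Leave 7.3.3 without a window: tying it to a set number of days after each procedure would narrow a rule that now has no limit.
5. Optionally, ask about reactions to the challenge when the patient returns the 6-hour urine jug. Diarrhea and cramping also appear in the RTOG scales, so a direct question helps to separate the two sources.

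The cost is a wording amendment to 7.3, one optional question at a contact that already takes place, and slightly more event reports. No visits are added.

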8. PHARMACEUTICAL INFORMATION

Intestinal permeability tests are commercially available and contain lactulose and mannitol. The patient will fast over night for 8 hours and will then drink a "challenge" drink supplied by Genova Diagnostics composed of 5gm of lactulose and 1gm of mannitol.

8.1 Lactulose

[figure not shown]
- Chemical Information

Chemical name: 4-O-beta-D-galactopyranosyl-D-fructofuranose

Molecular Formula: C₁₂H₂₂O₁₁

Molecular weight: 342.30

Chemical structure:

- Supplied by : commercially available from Genova Diagnostics
- Dosage and Administration: The lactulose and mannitol test is to be administered after at least a six hour fast. A glass of water is drunk just prior to ingesting the lactulose and mannitol and each hour for the first two hours. Urine is collected for six hours.
- Drug-related side effects: Diarrhea, gas, vomiting, cramping if ingested in significant quantities. Hypernatremia and hypokalemia after repeated dosing.

- Drug interactions: Lactulose is minimally absorbed and is primarily excreted in the feces or metabolized by enteric bacteria.
 - Acenocoumarol (moderate, probable)
 - Dicumarol (moderate, probable)
 - Droperidol (major, theoretical)
 - Levomethadyl (major, theoretical)
 - Licorice (major, theoretical)
 - Phenprocoumon (moderate, probable)
 - Warfarin (moderate, probable)
- Pregnancy category: B

8.2 Mannitol

[figure not shown]
- Chemical Information

Chemical name: hexan-1,2,3,4,5,6-hexol

Molecular Formula: C₆H₁₄O₆

Molecular weight: 182.172

Chemical structure:

- Supplied by : commercially available from Genova Diagnostics
- Dosage and Administration: The lactulose and mannitol test is to be administered after at least a six hour fast. A glass of water is drunk just prior to ingesting the lactulose and mannitol and each hour for the first two hours. Urine is collected for six hours.
- Drug-related side effects: typically with intravenous administration.
 - Cardiovascular: Chest pain, Hypotension, Palpitations, Tachyarrhythmia
 - Endocrine metabolic: Disorder of fluid AND/OR electrolyte, Hypernatremia, hyponatremia, hyperkalemia, acidosis
 - Gastrointestinal: Diarrhea (typically after greater than 20gm oral load), Nausea, Vomiting, Xerostomia
 - Neurologic: Headache, seizure
 - Respiratory: Rhinitis, pulmonary edema (rare)
 - Renal: Renal failure (rare), Urinary retention
- Drug interactions: Mannitol is a common food additive in candies for people with diabetes.
 - Arsenic Trioxide (major, theoretical)
 - Droperidol (major, theoretical)
 - Levomethadyl (major, theoretical)
 - Licorice (moderate, probable)
 - Sotalol (major, probable)
- Pregnancy category: C

Appendix IA
Protocol #06-C-
Specimen Collection Flowsheet

Patient Name: _____	Tumor site: _____	XRT start date: _____
Gender: (M/F) _____	Tumor histology: _____	XRT completion date: _____
Age (yrs): _____	Tumor stage: _____	HIV date: _____ Result: (+/-)
Baseline GI fxn: _____	Date resection/biopsy: _____	Hepatitis B/ C date: _____ Result: (+/-)
Other therapies/ abd surg/ dates: _____		

Date	Time	XRT Target	Baseline ¹	Prexrt ¹ (0)	COT	1-month F/U	3-month F/U	6-month F/U	12-month F/U	24 month F/U	36 month F/U
Blood											
Research EDTA*	10:00										
Research SST*	24:00 (11x380)										
Clinical											
Other											
Total blood (cc)											
Urine											
Research-cup*	15cc										
Other											
Stool	100gm										
Intestinal Permeability (6hour urine)											
PE											
RTOG											

¹Baseline and pre-xrt may be the same if xrt is the initial treatment
² CBC, ALT, AST, total bilirubin, serum BUN, serum creatinine

* Deliver to [name] lab
 [name]
 [name]

